7.2. Pre-Medication

In Phase I studies, some patients experienced infusion-related reactions to imetelstat, including but not restricted to allergy/hypersensitivity reaction (e.g., rash, fever, urticaria, dyspnea, bronchospasm, chills/rigors, myalgias, headache, fatigue, nausea and/or vomiting) during or within 24 hours of an infusion. Reactions were sporadic in nature and did not occur at a higher frequency with the first administration of imetelstat. These reactions were usually mild to moderate and generally resolved with slowing or interruption of the infusion and with supportive care (diphenhydramine, corticosteroids, and/or IV saline). The mechanism is not entirely clear but may involve complement activation. (See Section 8 for the Infusion reaction guidelines and [Appendix E](#).)

All patients will require premedication with diphenhydramine (25–50 mg, PO or IV) and hydrocortisone (100 mg PO or IV) or equivalent before receiving imetelstat.

8. DOSAGE MODIFICATION BASED ON ADVERSE EVENTS

8.1. Retreatment Criteria

Subjects may receive treatment for a maximum of 9 cycles during the “Core Phase” of the study. Subjects may be allowed to continue therapy beyond 9 cycles in an “Extension Phase” of the study if they do not meet any of the withdrawal criteria, do not have disease progression and are receiving some clinical benefit, at the discretion of the principle investigator. Patients may continue to receive imetelstat study treatment for as long as they derive clinical benefit or until study end. The study will end when all subjects have discontinued study drug, the last patient enrolled has been treated for 5 years, or imetelstat is commercially available in the United States, whichever occurs first.

Patients will be evaluated for safety and efficacy at the end of each cycle during both the core and extension phases of the study.

8.2. Dose Reduction

Once the need for dose reduction has been established (as per [Table 11](#)), treatment with imetelstat may be restarted, after reversal of drug-related toxicity (as per [Table 11](#)), with one level dose reduction, for patients receiving treatment every 21 days (see [Table 10](#)), or an increase in dosing interval (using the same drug dose) in patients receiving the drug every week; in the latter instance, dosing frequency is first increased to every two weeks and then to every 3 weeks, in case of recurrent toxicity that requires dose reduction (see [Table 9](#)). Once a dose reduction has been instituted, the dose should not be re-escalated.

Table 9: Dose Reductions

Dose Frequency	Action
Once weekly	Reduce to once every 2 or once every 4 weeks at same dose level (dose level might also be decreased per physician discretion per Table 10)
Once every 2 weeks	Reduce to once every 4 weeks at same dose level (dose level might also be decreased per physician discretion per Table 10)
Once every 3 weeks	Reduce one dose level per Table 10
Once every 4 weeks	Reduce one dose level per Table 10

Table 10: Dose Levels (Based on Adverse Events in Table 9)

Dose Level	All arms
0 ¹	9.4 mg/kg D1
-1	7.5 mg/kg D1
-2	6 mg/kg D1

¹ Dose level 0 refers to the starting dose (except Arms E and G).

Table 11: ALERT: Serious Adverse Event (SAE) reporting may be required for some adverse events (See Section 10)

ADVERSE EVENT/ laboratory test abnormality (must be at least possibly related to drug to qualify as a dose-modifying event)	AGENT	ACTION ¹
AT TIME OF RETREATMENT (i.e. imetelstat infusion beyond Day 1, Cycle 1)		
Absolute neutrophil count (ANC) <1.0 x 10 ⁹ /L	Imetelstat	Hold imetelstat. ² Restart at the next lower dose level (see Section 8.2), once ANC recovers to ≥1.0 x 10 ⁹ /L
Platelet count <50 x 10 ⁹ /L	Imetelstat	Hold imetelstat. ² Restart at the next lower dose level (see Section 8.2), once platelet count recovers to ≥50 x 10 ⁹ /L.
Absolute neutrophil count (ANC) <1.5 x 10 ⁹ /L and also associated with >75% drop from ANC recorded at Day 1 of the previous cycle	Imetelstat	Hold imetelstat. ² Restart at the next lower dose level (see Section 8.2), once ANC recovers to ≥1.5 x 10 ⁹ /L
Platelet count <100 x 10 ⁹ /L and also associated with >75% drop from platelet count recorded at Day 1 of the previous cycle	Imetelstat	Hold imetelstat. ² Restart at the next lower dose level (see Section 8.2), once platelet count recovers to ≥100 x 10 ⁹ /L.
SGOT (AST) and SGPT (ALT) ≥ Grade 3	Imetelstat	Hold imetelstat. Restart at the next lower dose level see Section 8.2), if recovered to Grade 1 or less (or to pre-study baseline).
Total Bilirubin >3.0 mg/dL (or direct bilirubin 1≥ mg/dL)	Imetelstat	Hold imetelstat. Restart at the next lower dose level (see Section 8.2), if recovered to Grade 1 or less (or to pre-study baseline).
Creatinine >3.0 mg/dL	Imetelstat	Hold imetelstat. Restart at the next lower dose level (see Section 8.2), if recovered to Grade 1 or less (or to pre-study baseline).

ADVERSE EVENT/ laboratory test abnormality (must be at least possibly related to drug to qualify as a dose-modifying event)	AGENT	ACTION ¹
Allergic Reaction Grade 2	Imetelstat	Hold imetelstat. Restart at the next lower dose level if adverse event reduced to \leq Grade 1. Discontinue imetelstat if event reoccurs at lower dose.
Allergic Reaction Grade 3	Imetelstat	Discontinue imetelstat and go to event monitoring per Section 4
Any Grade 3 ³	Imetelstat	Hold imetelstat. Restart at the next lower dose level (see Section 8.2), if adverse event reduces to \leq Grade 2.
Any Grade 4 ⁴		Hold imetelstat. Restart at the next lower dose level (see Section 8.2), if adverse event reduces to \leq Grade 2.

¹ Use the following to describe actions in the Action column:

- Omit = The current dose(s) for the specified drug(s) during a cycle is skipped. The patient does not make up the omitted dose(s) at a later time
- Hold/Delay = The current dose(s) of all drugs during a cycle is delayed. The patient does make up the delayed dose(s) when the patient meets the protocol criteria to restart drugs. Hold for maximum of 28 days, and then contact principal investigator and medical monitor.
- Discontinue = The specified drug(s) are totally stopped.

² Not required for cohort D.

³ Except fatigue, nausea, vomiting, diarrhea and hyperuricemia that persist despite treatment with optimal anti-diarrheals or anti-emetics. Such toxicity will be taken into account, for dose holding only when it persists despite appropriate treatment.

⁴ Except Grade 4 uric acid toxicity. Such toxicity will be taken into account for dose holding only when refractory to appropriate treatment.

In addition to any of the above toxicities, in the event of a drug-related Grade 2 or higher toxicity that the patient cannot tolerate or at the discretion of the Investigator, dosing may be reduced.

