7.1.1.1. Arm A Treatment Schedule

(Arm A permanently closed to accrual)

Agent	Dose	Route	Day	Cycle (ReRx) ± 3 days ¹
Imetelstat	9.4 mg/kg	IV as 2 hour infusion	1 ^{2,3}	Every 21 days

¹ Patients may continue to receive imetelstat study treatment for as long as they derive clinical benefit or until study end. The study will end when all subjects have discontinued study drug, the last patient enrolled has been treated for 5 years, or imetelstat is commercially available in the United States, whichever occurs first.

² If the patient has not achieved a CR or PR, by the end of Cycle 6, the dosing frequency may be increased to up to weekly using the **current dose level** at the discretion of the Investigator. The patient must be tolerating the current dose level without significant toxicity. Increase in dosing frequency is only allowed after Cycle 6. The cycle length will be 21-28 days. If the dosing frequency is increased to once weekly, the cycle length will remain 21 days. If the dosing frequency is increased to once every 2 weeks, the cycle length will be 28 days.

³ For patients whose response has plateaued for a minimum of 3 months, the dosing frequency may be reduced after Cycle 6 and the cycle length will be the length of the dosing interval. For example, if the dosing frequency is decreased to once every 3 months, the cycle length will be 84 days. Dosing can also be interrupted until relapse and restarted, in such patients, per physician discretion. In the case of interruption, a cycle will be 3 months while treatment is held and the patient will restart at the dose level/schedule they were receiving at the time of interruption.

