7.1.1.2. Arm B Treatment Schedule

(Arm B permanently closed to accrual)

Induction: Cycle 1				
Agent	Dose	Route	Day	Cycle (ReRx) ± 3 days
Imetelstat	9.4 mg/kg	IV as 2 hour infusion	1, 8, 15	Cycle 1 is 21 days
Maintenance: Cycles 2 and beyond ¹				
Agent	Dose	Route	Day	Cycle (ReRx) ± 3 days
Imetelstat	9.4 mg/kg	IV as 2 hour infusion	1 ^{2,3}	Every 21 days (Cycles 2 and beyond)

¹ Patients may continue to receive imetelstat study treatment for as long as they derive clinical benefit or until study end. The study will end when all subjects have discontinued study drug, the last patient enrolled has been treated for 5 years, or imetelstat is commercially available in the United States, whichever occurs first.

² If the patient has not achieved a CR or PR, by the end of Cycle 6, the dosing frequency may be increased to up to weekly using the **current dose level** at the discretion of the Investigator. The patient must be tolerating the current dose level without significant toxicity. Increase in dosing frequency is only allowed after Cycle 6. The cycle length will be 21-28 days. If the dosing frequency is increased to once weekly, the cycle length will remain 21 days. If the dosing frequency is increased to once every 2 weeks, the cycle length will be 28 days.

³ For patients whose response has plateaued for a minimum of 3 months, the dosing frequency may be reduced after Cycle 6 and the cycle length will be the length of the dosing interval. For example, if the dosing frequency is decreased to once every 3 months, the cycle length will be 84 days. Dosing can also be interrupted until relapse and restarted, in such patients, per physician discretion. In the case of interruption, a cycle will be 3 months while treatment is held and the patient will restart at the dose level/schedule they were receiving at the time of interruption.

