7.1.1.4. Arms E and G Treatment Schedule

(Arms E and G permanently closed to accrual)

Induction Cycle 1 and 2 Dosing				
Agent	Dose	Route	Day	Cycle (ReRx) ± 3 days
Imetelstat	7.5 mg/kg	IV as 2 hour infusion	1	Cycle is 28 days
Maintenance: Cycles 3 and beyond ¹				

¹ Patients may continue to receive imetelstat study treatment for as long as they derive clinical benefit or until study end. The study will end when all subjects have discontinued study drug, the last patient enrolled has been treated for 5 years, or imetelstat is commercially available in the United States, whichever occurs first.

If any **one** of the following criteria is met at the end of Cycle 2, then follow the [Table 5](#) dosing schedule below. If no criteria are met, follow the instructions below.

- Greater than 75% reduction in leukocyte count
- Greater than 75% reduction in platelet count
- Greater than 50% reduction in spleen size in patients with baseline palpable splenomegaly of >5 cm
- Greater than 2 gm/dL increase in hemoglobin level from baseline without transfusions

Table 5: Arms E and G Dosing if Criteria met = Yes

Agent	Dose	Route	Day	Cycle (ReRx) ± 3 days
Imetelstat	7.5 mg/kg	IV as 2 hour infusion	1 ^{1,2}	Cycle is 28 days

¹ In patients who do not achieve CR or PR by the end of Cycle 4, the frequency of dosing may be increased to every week or every two weeks, at the physician's discretion

² For patients whose response has plateaued, without signs of further improvement, for a minimum of 3 months, dosing frequency may be reduced to every 2 to 3 months, or treatment may be interrupted until relapse and restarted, at the physician's discretion. In the case of interruption, a cycle will be 3 months while treatment is held and the patient will restart at the dose level/schedule they were receiving at the time of interruption.

Criteria met = No

Treat as specified in Arm F (Cycle 3 will start with Cycle 1 of Arm F dosing schedule)

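### After recurrent toxicity on two-weekly dosing, the Section 8.2 paragraph sends patients who began weekly to every 3 weeks, but Table 9 sends them to every 4; the reach is limited and no statistical quantity changes

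*Protocol*

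**What the plan says.** Protocol Section 8.2 gives the rule for restarting imetelstat after drug-related toxicity in two places.

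- **Paragraph.** Patients on a 21-day schedule drop one dose level. Patients on weekly dosing keep the dose and have the interval lengthened: "dosing frequency is first increased to every two weeks and then to every 3 weeks", the second step being for toxicity that recurs. The sentence ends by citing Table 9.
- **Table 9, weekly row.** "Reduce to once every 2 or once every 4 weeks at same dose level".
- **Table 9, two-weekly row.** "Reduce to once every 4 weeks at same dose level".
- **Table 9, three-weekly and four-weekly rows.** The dose level falls by one and the interval does not change.

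The weekly and two-weekly rows also let the physician lower the dose level. Most Table 11 rows refer back to Section 8.2 for what the next lower level means.

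Weekly dosing arises as follows.

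- **Arm D (Section 7.1.1.3).** Days 1, 8, 15 and 22 of a 28-day cycle.
- **Arm B (Section 7.1.1.2).** Days 1, 8 and 15 of induction, where "Cycle 1 is 21 days"; every 21 days from Cycle 2.
- **Arms A and B without CR or PR by the end of Cycle 6 (Sections 7.1.1.1 and 7.1.1.2).** "the dosing frequency may be increased to up to weekly using the" current dose level.
- **Arms E and G on the Table 5 schedule without CR or PR by the end of Cycle 4 (Section 7.1.1.4).** "the frequency of dosing may be increased to every week or every two weeks". Patients in these arms who miss the Cycle 2 criteria are handled differently: "Treat as specified in Arm F".

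**The concern.** The paragraph offers Table 9 as its own detail, yet the two give different instructions. They agree that every 2 weeks is a permitted first step. They disagree on the second step (3 or 4 weeks) and on whether a weekly patient may go straight to every 4 weeks.

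This rule governs re-exposure after a toxicity judged at least possibly due to the drug. Two patients with the same history could be given different default dose intensities, each in line with one half of Section 8.2 and at odds with the other. The same ambiguity carries into the listings of dose adjustments and major deviations in SAP Sections 3.3 and 3.4, because either move departs from one of the two texts.

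**Working it through.** There is no figure in the plan to reproduce. The check is a comparison of texts, followed by simple arithmetic for size.

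**Step 1. The two texts side by side**

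| Current frequency | Section 8.2 paragraph | Table 9 |
|---|---|---|
| Weekly | every 2 weeks | every 2 or every 4 weeks |
| Every 2 weeks, toxicity recurs | every 3 weeks | every 4 weeks |
| Every 3 weeks | one dose level down (21-day patients) | one dose level down |
| Every 4 weeks | not addressed | one dose level down |

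Every 3 weeks appears in Table 9 only as a frequency the patient is already on.

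**Step 2. Is there a tie-breaker?** Sections 7.1.1.1 to 7.1.1.5, Table 11 and its footnotes, and Section 8.2.1 contain none. Both texts are current wording. The amendment log shows that Amendment 13 changed this section only by adding the ban on re-escalation.

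**Step 3. Who can meet the conflict?**

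- **Arm D:** weekly by schedule. A Table 11 footnote makes the neutrophil and platelet holds not required in this arm, so the conflict arises from the remaining rows.
- **Arms A and B:** only if escalated to weekly after Cycle 6.
- **Arms E and G:** only on the Table 5 schedule and escalated to weekly after Cycle 4. Patients moved to Arm F dosing are outside the point.
- **Arm B, Cycle 1:** marginal. There are three weekly doses, and from Cycle 2 the schedule is already every 21 days. Mainly the direct move to every 4 weeks differs.
- **Arm C:** not counted. Its 11 slots were treated on the Arm A or Arm B schedule (Protocol Section 7.1.1.3; SAP Section 2.4).

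**Step 4. Size.** Inputs: 9.4, 7.5 and 6 mg/kg from Table 10, with 7.5 mg/kg as the Arm E and G starting dose from Section 7.1.1.4. Intensity = dose ÷ interval in weeks.

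| Step | Paragraph (mg/kg/week) | Table 9 (mg/kg/week) | Table 9 ÷ paragraph |
|---|---|---|---|
| First, 9.4 mg/kg | 9.4/2 = 4.70 | 4.70, or 9.4/4 = 2.35 | 1.00 or 0.50 |
| Second, 9.4 mg/kg | 9.4/3 = 3.13 | 9.4/4 = 2.35 | 0.75 |
| Third, 7.5 mg/kg | 7.5/3 = 2.50 | 7.5/4 = 1.88 | 0.75 |
| First, Arms E and G, 7.5 mg/kg | 7.5/2 = 3.75 | 3.75, or 7.5/4 = 1.88 | 1.00 or 0.50 |
| Second, Arms E and G, 7.5 mg/kg | 7.5/3 = 2.50 | 7.5/4 = 1.88 | 0.75 |
| Third, Arms E and G, 6 mg/kg | 6/3 = 2.00 | 6/4 = 1.50 | 0.75 |

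The second-step ratio is (1/4) ÷ (1/3) = 0.75 at any dose. Over 12 weeks at 9.4 mg/kg, the paragraph gives 12/3 = 4 infusions, or 37.6 mg/kg. Table 9 gives 12/4 = 3 infusions, or 28.2 mg/kg.

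**The case against.** The case for leaving this alone has four parts.

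- **Discretion.** Table 9 allows an added dose-level cut, and the text under Table 11 lets the investigator reduce dosing for intolerable Grade 2 or higher toxicity or on judgement. Lower intensity is partly available whichever text is followed.
- **Reach.** This is one centre. All arms closed to accrual on 22 January 2014 with 80 patients enrolled. Only Arm D is weekly throughout by schedule; Arms A, E and G enter through optional escalation, and so does Arm B apart from Cycle 1.
- **Statistics.** Nothing in the primary analysis depends on the interval.
- **Table over text.** Table 9 is the fuller statement, and a careful reader might simply follow it.

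The second and third parts stand, and they keep the point small. The first does not remove it: discretion to go lower does not say which interval is the default. Nor does the fourth: the paragraph is just as explicit for weekly patients, and no sentence ranks the two. Closed accrual does not make the rule idle either, since Section 8.1 lets patients who benefit stay on drug until study end.

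A reader might go further and infer that a lengthened interval may later be shortened, because the ban reads "Once a dose reduction has been instituted, the dose should not be re-escalated" and names only the dose. The documents do not support making that a separate fault. Table 9 is titled as a table of dose reductions and its interval rows are worded as reductions, so the ban is most naturally read as covering interval changes too. The same reading applies to the permanence rule for liver enzyme elevations in Section 8.2.1.

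**Conclusion.** The inconsistency is real and sits in the current text. For patients who start from weekly dosing, Section 8.2 gives two second-step intervals and two views of the direct move to every 4 weeks, with no rule to choose between them. The default intensity differs by 25% at the second step (3.13 against 2.35 mg/kg/week at 9.4 mg/kg), and by 50% at the first step if Table 9's direct move is used.

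These figures assume full doses given on time at the stated level. The documents do not say how many patients were dosed weekly, so the number affected cannot be given.

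A reader might infer that the response results or the operating characteristics of the design are compromised. They are not: response is defined without reference to dosing interval, and the decision rules rest on counts of responders. This is a fault in a dosing instruction that bears on patient safety. It is worth correcting, and its reach is limited.

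**What to change.** Keep Table 9 as it is. It covers every frequency and gives the lower intensity after toxicity. Change the Section 8.2 paragraph so that, for weekly patients, the interval is first lengthened to two weeks (or directly to four weeks if the physician so decides), and then to four weeks if toxicity calling for reduction recurs, still citing Table 9. Writing that the *interval* is *lengthened* also removes the present slip of calling a longer interval an increased frequency.

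Do not resolve it by rewriting the two-weekly row of Table 9 to lead to every 3 weeks. That row also governs patients in Arms A, B, E and G who were escalated directly to every 2 weeks. The paragraph does not address them, so they have no conflict now and their rule would change without reason. Splitting the answer by arm on the ground that Arms A and B run 21-day cycles is not sound either, because those arms use a 28-day cycle once dosed every 2 weeks (Sections 7.1.1.1 and 7.1.1.2, footnote 2).

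The cost is one clinical confirmation by the sponsor and one sentence. The downside is that patients who would have gone to every 3 weeks under the paragraph receive 25% less drug at that step: at 9.4 mg/kg, 28.2 rather than 37.6 mg/kg over 12 weeks.

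### Protocol Table 11, footnote 3 contradicts itself on whether a Grade 3 nausea, vomiting or diarrhea event that persists despite treatment leads to a dose hold

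*Protocol*

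**What the plan says.** Table 11 in Protocol Section 8.2 lists the events, at least possibly related to drug, that modify dosing when a patient comes for any infusion after Day 1 of Cycle 1. For any Grade 3 event the action is "Hold imetelstat. Restart at the next lower dose level (see Section 8.2), if adverse event reduces to" Grade 2 or lower.

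Footnote 3 qualifies that row in two sentences:
- Sentence 1: "Except fatigue, nausea, vomiting, diarrhea and hyperuricemia that persist despite treatment with optimal anti-diarrheals or anti-emetics".
- Sentence 2: "Such toxicity will be taken into account, for dose holding only when it persists despite appropriate treatment".

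The neighbouring footnote 4 qualifies the Grade 4 row: "Except Grade 4 uric acid toxicity. Such toxicity will be taken into account for dose holding only when refractory to appropriate treatment".

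A closing clause below the footnotes separately permits a reduction, on this condition: "in the event of a drug-related Grade 2 or higher toxicity that the patient cannot tolerate or at the discretion of the Investigator, dosing". The opening paragraph of Section 8.2 says that a dose, once reduced, is not to be raised again.

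**The concern.** A dose-hold rule has to give one answer for one event. Here the same circumstance, persistence in spite of treatment, is the ground for leaving an event out in sentence 1 and the ground for counting it in sentence 2. Two clinicians could each follow one sentence faithfully, and one would hold the drug while the other would not.

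Because the row joins the hold to a restart at a lower level, and Section 8.2 bars re-escalation, the choice of sentence can alter a patient's exposure for the rest of treatment. The rule also outlived accrual: all arms closed on 22 January 2014, but Section 8.1 lets patients stay on imetelstat while they benefit, until study end. Footnote 2 releases Arm D only from the blood-count holds, so footnote 3 applies in every arm.

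**Working it through.** No arithmetic decides this point. The check sets the two sentences against each possible course of a listed Grade 3 event, with the row's default action (hold, then reduce) as background.

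| Course of the event | Sentence 1 | Sentence 2 |
|---|---|---|
| Persists despite treatment | Excepted from the row: no hold | Counts: hold |
| Responds to treatment | Not excepted, so the default hold applies (inferred) | Does not count: no hold |

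**Persistent events.** Both sentences speak directly to this case and disagree.

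**Events that respond.** Sentence 1 does not mention them. Their place in the hold row follows only because they are not excepted. The conflict here also depends on what sentence 2 refers back to. If it refers to the listed event types in general, it conflicts with the default row. If it refers only to the persistent events just named, its condition is always met, it cancels the exception, and the footnote changes nothing. Neither reading gives a working exception.

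**The five event types.** The condition in sentence 1 is failure of optimal anti-diarrheals or anti-emetics. That fits diarrhea, nausea and vomiting. It does not fit fatigue or hyperuricemia, which those drugs do not treat, so for these two the exception has no usable condition.

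**Footnote 4 as comparator.** It has the same two-part form, but its exception names the event without a persistence qualifier, so its second part can restrict the exception without contradicting it. The defect in footnote 3 is therefore its own and not a feature of the format.

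**Other text that might settle it.**
- The closing clause of Section 8.2 permits a reduction on intolerance or at discretion, but does not say whether the Table 11 hold applies.
- Section 9 covers supportive care for diarrhea, including Grades 3 and 4, and is silent on holding imetelstat.
- Section 13 allows discontinuation for adverse events and does not address holds.

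**Likely frequency.** Section 1.3.4.7 puts Grade 3 diarrhea and nausea each below 2% in earlier experience. If that carried over to the 80 patients enrolled here (Section 16.1), each would occur in fewer than 0.02 × 80 = 1.6 patients. That is an assumption, since the populations and schedules differ. Section 1.4.1 also reports no Grade 3 or 4 non-hematologic toxicity in the first 22 patients (11 each in Arms A and B), with follow-up still short: most of the Arm A patients had at least 3 cycles. Fatigue was the most frequent Grade 3 constitutional event, without a stated rate. No Grade 3 rate is given for vomiting or hyperuricemia.

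**The case against.** The best defence is that this is a misplaced clause whose sense a careful clinician would recover from footnote 4, in a single-center trial with one investigator team. The comparison does point to a drafting slip, and the single center does reduce the room for divergent practice. But nothing in the protocol tells the reader to interpret one footnote through the other, and a safety hold should not depend on such an inference.

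A second defence divides sentence 2 after the word only, so that persistent events lead to a hold without a reduction. That would remove the literal clash for persistent events. It needs a break that the punctuation does not mark, and it would give an event that responded to treatment a heavier consequence than one that did not. Footnote 4 uses the same phrase with no such sense.

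The objections to scope largely succeed. A reader might infer that the sentences are exact opposites for all five event types, in both courses of the event. The documents do not support that, for the reasons in the working. In addition, Table 11 applies at retreatment, and Sections 1.3.4.6 and 1.3.4.7 say that these symptoms usually settle within about 7 days. On 21- or 28-day schedules an event that responded will often be gone by the next infusion. The weekly schedules (Arm B Cycle 1, Arms C and D) and the Day 1, 3 and 5 schedules leave less time, so the case is often moot rather than always.

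A reader might also take the general frequency of gastrointestinal events as the measure of impact. Section 1.3.4.6 says that most are Grade 2 or less, and footnote 3 concerns Grade 3 only.

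**Conclusion.** The point holds as an internal inconsistency within one footnote; it is not a questionable design choice. It is firm for Grade 3 nausea, vomiting and diarrhea that persist despite treatment. For fatigue and hyperuricemia the fault is a condition that cannot sensibly be applied. For events that respond, the conflict is inferential and often without practical effect.

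The number of patients is probably small, on the assumption that earlier Grade 3 rates are a fair guide. For a patient who is affected, the consequence can last, because a reduction is not reversed.

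It would be tempting to conclude that the trial's results are compromised. The documents give no ground for that. SAP Section 3.3 only lists dose adjustments and their reasons, with no planned summary or comparison of hold rates. The response definitions and exact intervals in SAP Section 4.2 do not use holds. The decision rules in Protocol Section 16.1 count responses, and the stopping rule in Section 16.8 counts Grade 4 non-hematologic events. No view is taken here on which sentence states the right clinical rule.

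**What to change.** Reword footnote 3 so that a single condition decides whether a listed Grade 3 event leads to a hold. State what happens when the condition is met and when it is not, and say whether a hold under this footnote carries the row's dose reduction. Give fatigue and hyperuricemia their own condition, separate from the wording about anti-diarrheals and anti-emetics. The sponsor physicians and the investigator decide the content of the rule.

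The cost is one reworded footnote and a notice to the treating team. No sample size, endpoint or analysis changes. If treatment under the footnote has already finished, the study report should say which reading was applied, so that the SAP Section 3.3 exposure listing can be interpreted.

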8.3. Infusion Reaction

The guidelines described in [Table 12](#) should be followed for managing imetelstat infusion reactions (See [Appendix E](#)).

Table 12: Guidelines for Managing Infusion Reactions

Infusion Reaction	Management Guideline
Grade 1 Mild and transient (e.g., mild flushing, rash, pruritis, fever)	
 • Evaluate and manage symptomatically as needed. • May complete infusion if reaction remains mild, with stable vital signs and does not worsen to Grade 2 or more.
Grade 2 Moderate (e.g., moderate flushing, rash, dyspnea, chest discomfort, hypotension)	
 • Stop infusion • Manage symptomatically: 
 – Administer diphenhydramine 25 mg and dexamethasone 10 mg IV, if required (particularly if not received within last 4 hours) – Consider IV fluids, acetaminophen, oxygen, bronchodilators etc. • After recovery, resume infusion at half the previous rate for 15 minutes 
 – If no further symptoms occur, complete the infusion at the full dose rate – If symptoms recur, discontinue imetelstat
Grade 3 Severe (not rapidly responsive to symptomatic medication and/or brief interruption of infusion; recurrence of symptoms following initial improvement; hospitalization indicated for other clinical sequelae (e.g., renal impairment, pulmonary infiltrates)	
 • Stop infusion • Administer supportive care as indicated 
 – Consider epinephrine, corticosteroids, diphenhydramine, IV fluids, acetaminophen, oxygen, bronchodilators, vasopressors, etc. • Discontinue imetelstat

Grade 4 Life-threatening (e.g., anaphylaxis, angioedema severe hypotension requiring vasopressors, respiratory distress requiring ventilator support)	
 Stop infusion Administer supportive care as indicated Discontinue imetelstat
--	--

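### Table 11 stops imetelstat for a Grade 3 allergic reaction but, read literally, lets a Grade 4 allergic reaction be re-treated at a lower dose, contrary to Table 12

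*Protocol*

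**What the plan says.** Protocol Section 8.2, Table 11, sets dose actions by event and grade for events at least possibly related to the drug.

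- **Allergic reaction, Grade 2:** hold, and restart one level lower once the event is Grade 1 or less. A recurrence rule follows: "Discontinue imetelstat if event reoccurs at lower dose".
- **Allergic reaction, Grade 3:** "Discontinue imetelstat and go to event monitoring per Section 4". Footnote 1 makes clear that discontinuing is a complete stop, not a hold.
- **Allergic reaction, Grade 4:** no row.
- **Any Grade 3 and any Grade 4 (two separate rows, same action):** hold. "Restart at the next lower dose level (see Section 8.2), if adverse event reduces to" Grade 2 or less. Footnote 4 qualifies the Grade 4 row with "Except Grade 4 uric acid toxicity" and excepts nothing else.

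Section 8.3 says that Table 12 "should be followed for managing imetelstat infusion reactions". Its Grade 4 category is "Life-threatening (e.g., anaphylaxis, angioedema severe hypotension requiring vasopressors, respiratory distress requiring ventilator support", and the action is to stop the infusion, give supportive care and discontinue imetelstat. Section 7.2 describes "infusion-related reactions to imetelstat, including but not restricted to allergy/hypersensitivity reaction", arising in the course of an infusion or in the 24 hours after it.

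**The concern.** A dose-modification table should not become more lenient as the event becomes more severe. Read as written, Table 11 does so for allergic reactions between Grade 3 and Grade 4. Someone who looks up a Grade 4 allergic event there finds permission to re-expose the patient, whereas a Grade 3 event would have ended treatment.

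The same event can also meet Table 12, which gives the opposite instruction. No sentence in the text reviewed says which table prevails.

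What is at stake is patient safety on re-challenge. Sample size, error rates and the primary analysis do not depend on it.

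**Working it through.** No arithmetic applies, and the plan states no figure to reproduce. The check sets the written rules side by side.

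| Event | Table 11 action | Highest grade at which restart is allowed | Stop on recurrence? | Table 12 action, if an infusion reaction |
|---|---|---|---|---|
| Allergic, Grade 3 | Discontinue | No restart | Not applicable | Discontinue |
| Allergic, Grade 4 (by default, catch-all row) | Hold, restart lower | 2 | No | Discontinue |
| Allergic, Grade 2 | Hold, restart lower | 1 | Yes | Not at issue here |

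**Step 1. Does the Grade 3 row mean Grade 3 or higher?** The wording does not support that. The liver-enzyme row of the same table reads "SGOT (AST) and SGPT (ALT) ≥ Grade 3", so the table uses the sign when it intends higher grades. It also lists the catch-all Grade 3 and Grade 4 rows separately although their actions are the same, which suggests that a bare grade means that grade alone. Grade 3 or higher was probably the intention, but the text does not say it.

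**Step 2. Does a specific-over-general reading close the gap?** It works at Grade 3, where an allergic row competes with the catch-all row. It cannot work at Grade 4, where there is no specific row to prefer.

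**Step 3. Compare the Grade 4 default with the two allergic rows.** The default is weaker than the Grade 3 row, which allows no restart. It is also looser than the Grade 2 row in two respects: restart is allowed at Grade 2 instead of Grade 1, and nothing stops treatment if the reaction recurs.

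**Step 4. Compare with Table 12.** The two tables agree at Grade 3 (discontinue) and part at Grade 4. Because Section 7.2 counts allergy and hypersensitivity among infusion-related reactions, a single anaphylactic event can fall under both.

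**Step 5. What would the restart dose be?** The catch-all row points back to Section 8.2. For weekly dosing, that section lengthens the interval at the same dose. Table 9 keeps the dose level for weekly and two-weekly schedules, with a reduction only at the physician's discretion. Weekly dosing is the schedule for Arms C and D and an allowed escalation in Arms A, B, E and G. In such patients the literal default could permit re-exposure at an unchanged mg/kg dose.

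**Step 6. How often could this matter?** The documents give no rate for Grade 4 allergic events outside infusion reactions. The 3% incidence of Grade 3 or 4 infusion-reaction signs and symptoms in Section 1.3.4.5 does not size the gap, because Table 12 already requires discontinuation at those grades.

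**The case against.** The strongest reply is that other text already covers nearly every real case.

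- **Table 12 governs infusion reactions.** The drug is given only by a 2-hour infusion, with a half-life of 4 to 5 hours (Section 15.1.5). Most serious allergic reactions would therefore fall in the Section 7.2 window and lead to discontinuation. This stands, and it is the main reason the point is minor.
- **Table 11 is a retreatment table.** Its rows apply when a further infusion is due, whereas Table 12 manages the acute event. A patient with anaphylaxis would already have been discontinued. This is a sensible reading and removes most of the conflict in practice, but the protocol does not state that order of precedence.
- **Nothing compels re-challenge.** Restart in Section 8.2 is permissive. Section 13 requires discontinuation once continuing is judged to be against the participant's interest. Section 10.4.1 requires an immediate call to the medical monitor for a life-threatening event attributed to the drug. All of this is correct. These are matters of judgement and reporting, however, whereas Grade 3 has a fixed rule.
- **The footnotes are weak evidence.** Footnote 3 does not except allergic reactions from the catch-all Grade 3 row either, although Grade 3 allergic reactions plainly have their own rule. This is fair: the missing Grade 4 row is the defect, and the footnote only confirms that nothing else fills the gap.
- **Appendix E, on anaphylaxis precautions, was not available for this review.** If it contains a fixed stop rule for Grade 4 allergic events, the second part of the concern falls away.
- **Few patients can be affected.** Enrolment closed on 22 January 2014 with 80 patients. This limits the reach but does not correct the rule.

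**Conclusion.** The concern holds, as a minor point. Two things remain:

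1. For Grade 4 allergic events that are also infusion reactions, Tables 11 and 12 give opposite instructions, and nothing in the text reviewed ranks them.
2. For Grade 4 allergic events not classed as infusion reactions, Table 11 gives the wrong default, and stopping depends on a best-interest judgement under Section 13.

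The size cannot be quantified from the documents, and the number of events in the second group may be 0. The conclusion rests on reading Table 11 by its wording, and on Appendix E containing no overriding rule. The statistical design and analyses are unaffected. No criticism is made of how Grade 2 infusion reactions are handled.

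**What to change.** Relabel the Grade 3 allergic row in Table 11 as Grade 3 or higher, keeping its present action (discontinue and move to event monitoring). This is the change that matters.

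Also add to footnotes 3 and 4 that allergic and infusion reactions are excepted from the catch-all rows and are managed by the allergic-reaction rows and Table 12. That settles precedence between the two tables.

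The cost is one row label and two footnotes in a protocol amendment, with no new data, visits or analyses. If no patient remains on treatment, correct the table before it is reused in another protocol.
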